- 6. To document implementation and health care provider and support group facilitator perspectives regarding intervention content and delivery to inform scalability and sustainability.

Methods

Design

This study will be a randomized controlled trial (RCT) of the SMART Connections, a socio-behavioral intervention using an online social media either platform (Facebook) designed to improve retention in HIV care services. Participants will be randomized to the online intervention group or control group.

The hypothesis being tested with this study is:

YLHIV who participate in SMART Connections will be more likely to be retained in HIV care at 12 months after enrollment than YLHIV in the control group.

Secondarily, we will also test the role of social support as a potential mediator of the intervention effects on retention in care:

Among YLHIV enrolled in ART services, those in the treatment group who are exposed to SMART Connections will have greater social support and, in turn, will be more likely to be retained in HIV care services at 12 months compared to those in the control group.

Structured questionnaires will be completed through face-to-face interviews with YLHIV participants at baseline, at six months, and at endline, which will occur after 12 months of participation. Clinical data on ART diagnosis, visits and biological tests (CD4 and viral load) will be abstracted from electronic patient medical records. At six months and endline, we will repeat the structured questionnaires from baseline, adding questions on participation and perspectives on the intervention. Additionally, in-depth interviews (IDI) with a subset of participants will be conducted at the completion of the intervention.

We will use a software program, Grytics, which is specifically designed to collect and analyze Facebook group data. We will collect data on the number of active members, the number of posts, the number of comments, and the number of reactions to posts by type ("wow," "love," "like," "angry," "haha," and "sad"), per session. We will also document the number and reason for personal messages to the group facilitator, such as question about side effects, question about appointment, etc. Monitoring the push messages from the group facilitator will also permit analysis of the degree of fidelity to the messages and delivery schedule that is implemented.

Intervention Description

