Each SMART Connections group will consist of approximately 15 to 20 YLHIV, and approximately 15 groups in total will be formed. Once a sufficient number of YLHIV have been recruited and randomized to form a group, the group will begin with an initial, in-person group meeting with the group facilitator. Online groups will be formed by local government area to ensure participants are able to travel to this initial meeting.

During this meeting, the participants will have an opportunity to meet one another, possibly for the first time, and the facilitators face-to-face. The intent and design of the intervention will be described and ground rules for participation will be set. Ground rules will be discussed and accepted by the group members, but at a minimum, group members will be advised not to talk about what is discussed in the online group with people outside of the group. A brief activity that highlights confidentiality and the consequences of breaking confidentiality will be implemented. During this meeting, the participants will also receive their study phones and the facilitator will record their contact information (telephone numbers, email addresses and Facebook ID). Those who prefer can use their existing sim card (in the study phone), phone or Facebook ID to participate in the project, as long as they are willing to provide the information to the facilitator to enable them to be enrolled in the group. The facilitator will enroll each participant into the virtual group, and then a demonstration of how to open, log-in, post comments and log-out of the group will be made. Each participant should demonstrate the ability to log in and out to the facilitator. The facilitator will also set conditions and expectations for responding to posts and messages by the facilitator, such as limiting his/her responses to group members to business hours and perhaps certain times of the day. Also, the facilitator will instruct the participants if they need to contact the facilitator individually, to send a message to call back when it is safe to do so without risk of breaking confidentiality and the facilitator will call the person.

For those participants who are randomized to the control arm, they will receive their study phone when they return for their next clinic visit.

Standard of care services

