Participants will be asked to respond to structured questionnaires through face-to-face interviews conducted by trained interviewers using computer tablets prior to the launch of the intervention, after completing the intervention sessions and at the end of the study period. Data to be collected include: basic demographic information (e.g. sex, age, education level, relationship status (e.g. married, partnered, single), living arrangements (whether they live with a parent or guardian, how many people are in their household, and relationship to those people), as well as contact information (phone number, place of residence); HIVrelated information including how long since diagnosis, current ART regimen, last CD4 and viral load test date and results, disclosure status, self-reported adherence; social support measures covering emotional, instrumental, informational and network social support dimensions; factors associated with poor retention and adherence, including depression/anxiety, alcohol and other substance use, and perceived and experienced stigma; and access to and use of mobile telephones and social media applications. Forms will be administered at baseline and again at six months and endline, which will be 6 and 12 months after the intervention is initiated, respectively. Six-month and endline questionnaires will include additional, closedand open-ended questions pertaining to intervention participation. Telephone interviews may be conducted in place of face-to-face interviews for participants who, after at least 2 attempts to schedule in-person interviews, are unable or unwilling to return to the clinic for interviews after the intervention and at the end of the study period.

Clinical data

A data abstraction sheet will be developed to abstract relevant clinical data for each study participant. Trained data collectors will abstract data periodically (approximately quarterly) through 15 months after enrollment. As noted, the form will only record the participant's unique study ID for identification purposes. Data to be abstracted will include: date and results of CD4 cell counts and viral load tests; date of HIV diagnosis; date of ART initiation; WHO clinical stage at ART initiation; dates of ART refills; dates of ART clinic visits.

Participation data

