We will collect basic demographic information on participants (sex, age, marital/relationship status, education, occupation, religion) as well as background information on the participant's HIV infection: when diagnosed, when started ART, disclosure of HIV status to others, viral load and CD4 testing. Additionally, we will collect data on psycho-social factors associated with poor retention and adherence, including depression/anxiety, alcohol and other substance use, and perceived and experienced stigma.

The measures for which data will be collected are outlined below, by study objective. A summary of the measures and source of data, by objective, is found below in Table 1.

Objective 1: To test the effectiveness of a structured online support group (SMART Connections) to retention in HIV services among YLHIV.

Retention: This main outcome is defined as retention in clinical HIV services and on treatment. We will abstract data from the clinic electronic medical record system on date of all visits, which are typically monthly, to ART services between enrollment and the endline of this study.

Retention is defined as having attended a scheduled HIV clinic visit within three months of the visit date. For our primary analysis, using a survival analysis approach, we will record the dates for all scheduled clinic visits for each participant, then follow the data up to three months from the date of the last visit attended. If a participant fails to return after a scheduled visit for more than three months, the date of the missed visit will be the date of loss to follow-up recorded, unless a death or transfer of service is documented.

We will also report on the proportion of participants, by study arm, who are retained at 12 months after enrollment. To be considered retained in HIV services, an individual must, at 12 months after enrollment, have picked up his/her medication for his/her most recently scheduled clinical follow-up visit within 3 months of the date when it was scheduled to take place. We will record, from the medical record, if a participant has knowingly enrolled in services elsewhere (transferred), in which case attempts to contact the participant will be made, if feasible; we will also record if the participant has died or has been recorded as lost to follow-up.

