This main outcome is defined as retention in clinical HIV services and on treatment, defined as having attended a scheduled HIV clinic visit within 4 weeks of the visit date. To be considered retained in HIV services at endline, an individual must, at endline, have picked up his/her medication for his/her most recently scheduled clinical follow-up visit within 4 weeks (28 days) of the date when it was scheduled to take place. "Endline" will be considered the date of the participant's endline interview, or, for those that did not participate in an endline interview, an approximate date based on the median length of time between baseline and endline for other participants enrolled in the same month. We will record, from the medical record, if a participant has knowingly enrolled in services elsewhere (transferred), in which case attempts to contact the participant will be made, if feasible; we will also record if the participant has died, defaulted, or has been recorded as lost to follow-up.

Cases that can be confirmed to have died or transferred to a facility outside the study facilities and retention data cannot be obtained reliably will be considered censored.

Nigeria's definition of retention in HIV services changed during the course of the study, to be more stringent (4 weeks vs. 12 weeks). We will therefore secondarily assess retention using the older, less stringent, definition.

Created variables will be defined as follows:

Analysis Plan: Using Social Media to improve ART Retention and Treatment outcomes among youth living with HIV in Nigeria - The Youth SMART study PHSC #1151489; Version 1.0; December 2019

ltfu_el - care status at EL

0=in care at EL

Latest visit (i.e. v5q036) +/- 28 days from today_el/today_el_approx actual visit (i.e. v5q036) more than 28 days before today_el/today_el_approx AND follow-up visit (i.e. v3q044) on or after today_el/today_el_approx

1=LTFU at EL

actual visit < today_el/today_el_approx + 28 days AND latest MRE on or after today el/today el approx

8=Transfer

transfer==1 AND q027 is before today_el/today_el_approx AND q027 is AFTER
the latest visit (i.e. v3q036)

9=Death

death == 1

.=Missing

Insufficient data to assess care status at endline. latest_mre is before today_el/today_el_approx AND latest follow-up date (i.e. v1q044) before today_el/today_el_approx

Retention for survival analysis

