For the survival analysis, we will create two sets of variables indicating retention using a 28 day cutoff and using a 90 day cutoff to reflect the fact that the national guidelines for retention in HIV services changed from 12 weeks (i.e. 90 days) to 4 weeks (i.e. 28 days). For each recorded visit, we will also assess whether the participant is within their scheduled window and the number of days between the scheduled visit date and the date the visit was actually attended (v1 denotes the first attended visit after study enrollment; v2, v3, v4, etc. will be calculated for all visits between study enrollment and date of EL questionnaire (or date EL questionnaire should have been conducted, based on enrollment date, for those LTFU in the study at endline):

For each visit, starting at visit 2 (i.e. v2):

- v2_days_aftersched = [visit date (v2q036)] [date of prior scheduled visit (v1q044)]; missing if either date is . or jan 1 1990
- v2_ltfu_28 = 1 if v1_days_aftersched >28; = 0 if v1_days_aftersched ≤28; missing if next scheduled visit date (v1q044) is missing (. or jan 1 1990).
- v2_ltfu_90 = 1 if v1_days_aftersched >90; = 0 if v1_days_aftersched ≤90; missing if next scheduled visit date is missing (. Or jan 1 1990).

1tfu 28 LTFU status for survival analysis using 28 day cutoff

- **ltfu_28**=1; lost to follow-up
 - o v2 ltfu 28==1 OR v3 ltfu 28==1 OR v4 ltfu 28==1, etc.
 - o Appears retained for all recorded visits, but earliest value of today_el, today_el_approx, latest_mre falls MORE than 28 days after latest instance of vnq044
- ltfu 28=0; retained

- o v2 ltfu 28==0 AND v3 ltfu 28==0 AND v4 ltfu 28==0, etc. AND the earliest value of today el, today el approx, latest mre falls within 28 days of latest instance of **vnq044**
- 1tfu 28=8; transferred out
 - o Retained up to the date of transfer (transfer==1 and q027, transfer date, must be non-missing)
- **ltfu 28**=9; died
 - o Retained up to the date of death (death==1 and q028, death date, must be non-missing)

1tfu 90 LTFU status for survival analysis using 90 day cutoff

- **ltfu 90**=1; lost to follow-up
 - o v2 ltfu 90==1 OR v3 ltfu 90==1 OR v4 ltfu 90==1, etc.
 - o Appears retained for all recorded visits, but earliest value of today el, today el approx, latest mre falls MORE than 90 days after latest instance of **vnq044**

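### Six-month and endline interviews are timed from the start of the intervention, a date controls do not have, so SAP endline status and the questionnaire outcomes could be compared after unequal time since baseline

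*Protocol*

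**What the plan says.** The documents give several starting points for the follow-up clock.

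- Protocol, Structured questionnaires: the six-month and endline forms come at times "which will be 6 and 12 months after the intervention is initiated, respectively".
- Protocol, Design: interviews are "at six months, and at endline, which will occur after 12 months of participation".
- Protocol, Measures, Objective 1: for the proportion retained, "an individual must, at 12 months after enrollment, have picked up his/her medication". This is read from clinic records.
- SAP IV.C, Retention for survival analysis: for people not interviewed, visits count up to the "date EL questionnaire should have been conducted, based on enrollment date".

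The protocol's Intervention Description says when the intervention starts: "Once a sufficient number of YLHIV have been recruited and randomized to form a group, the group will begin" with an in-person meeting. Groups of about 15 to 20 are formed within a local government area (LGA). Controls have no group start. They collect a study phone at their next clinic visit.

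The SAP (IV.C, Retention at endline) sets endline at the participant's own interview date. Without an interview it uses "an approximate date based on the median length of time between baseline and endline for other participants enrolled in the same month", with no separation by arm. The same dates limit the visit count, and they are among the dates that can close follow-up in the survival variables.

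**The concern.** A rule tied to intervention initiation cannot be applied to a control without a substitute date, and neither document names one. Enrolment is the natural choice, because the protocol's other sections and the SAP's due date point to it. If a site does that, an intervention participant whose group took some weeks to fill is interviewed that much later after baseline than a control enrolled on the same day.

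Because the SAP reads care status on the interview date, the arms would be classified after different exposure to loss. Four results depend on that date:

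- endline care status (ltfu_el);
- retention at endline as the outcome of the mediation models (SAP, Objective 3);
- cost per participant retained (SAP, Objective 4);
- changes in social support and knowledge, and self-reported adherence, all taken at the endline interview (SAP, Objective 2).

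Later reading lowers measured retention and raises visit counts in the intervention arm, and neither effect is due to the intervention. The fallback date does not repair this. A median pooled over arms would fall earlier than the endline of interviewed intervention peers and later than that of interviewed control peers.

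**Working it through.** **1. Reproduce the plan's rates and sample size.** Inputs (protocol, Sample size): 12-month retention 0.45 and 0.575, exponential times, 10% loss, two-sided 5%, 80% power.

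- Monthly rates: −ln(0.45)/12 = 0.0665 (control); −ln(0.575)/12 = 0.0461 (intervention). Hazard ratio = ln(0.575)/ln(0.45) = 0.693, stated as 0.69.
- Events (Schoenfeld): 4 × (1.960 + 0.842)² / (ln 0.693)² = 234.
- With exponential loss of 10% by month 12 (0.00878 per month), the event probabilities are 0.526 and 0.405, mean 0.4655. Per arm: 234 / 0.4655 / 2 = 252, against the stated 250. Power at 250 per arm is 0.799.

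The figure reproduces and does not depend on the interview anchor. The rates can be used for step 3.

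**2. An assumed wait.** The documents state no lag. Assumptions:

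- Accrual is even over 8 weeks (the point at which the Sampling procedure changes method) to 12 weeks (three enrolment months in the Timeline).
- Treatment-arm numbers by LGA come from the facility table: 44, 27, 18, 50, 38, 40 and 34 for Calabar. Calabar is split 39:60 by eligible patients into 13.4 and 20.6.
- Groups fill in sequence, with k = 3, 2, 1, 3, 2, 2, 1, 1 groups (15 in total, the protocol's approximate number).

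If an LGA fills k groups in sequence, the mean wait is 1/(2k) of the accrual period. Weighted over LGAs: Σ n/(2k) / Σ n = 67.9 / 251 = 0.27. This is 15 days for 8 weeks and 23 days for 12 weeks. Treating Calabar as one area with two groups gives 0.24, or 13 to 20 days.

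**3. Effect on cumulative retention.** Drop = S(T) − S(T + w), where S(t) = exp(−rate × t).

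| Endline T after enrolment | Intervention rate, w = 15 to 23 days | No true effect (control rate), same w |
|---|---|---|
| 12 months | 1.3 to 1.9 points | 1.5 to 2.2 points |
| 9 months | 1.5 to 2.2 points | 1.8 to 2.7 points |
| 6 months | 1.7 to 2.6 points | 2.2 to 3.3 points |

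The 6- and 9-month rows are shown because the SAP places the primary outcome at 6 to 9 months. The planned difference at 12 months is 12.5 points.

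**4. Slower late loss.** The protocol's Background reports 2,939 of 6,648 youth lost, two-thirds of them within three months of starting treatment. A crude rate that ignores censoring and puts the whole remaining third into months 3 to 12 is ln(4,689 / 3,709) / 9 = 0.026 per month, against 0.046 above. The 12-month drop becomes 0.575 × (1 − exp(−0.026 × w/30.4)) = 0.7 to 1.1 points.

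**5. What does not move.** The proportion retained 12 months after enrolment (protocol, Measures; SAP, Objective 1) does not use the interview date. The log-rank test starts at the baseline survey and stops at day 270 in both arms (SAP IV.C and Objective 1). The interview date enters only as one of the dates that can close follow-up earlier.

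**The case against.** The strongest reply is that unequal timing is not planned anywhere. The questionnaire section states one rule for everyone, and its surrounding wording can be read as a single study-wide launch. With one launch date, time since enrolment would vary between people but not systematically between arms. The Data collection section schedules both arms at routine clinic appointments, and the SAP's due date and fallback median both look to enrolment.

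Part of this stands: no sentence tells sites to time controls from enrolment and intervention participants from group launch, so the imbalance is conditional. The single-launch reading is harder to sustain, because about 15 groups each start when they fill. The Timeline (an extracted table, so read with care) gives seven months for sessions lasting 4 to 4.5 months, which implies starts spread over some 2.5 to 3 months. The clinic-appointment rule says where an interview happens, not which month is due.

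The objections to size also stand. The facility numbers are labelled illustrative. Some of the assumed groups fall below 15 members, and even accrual is a guess. The exponential model describes first loss, whereas ltfu_el is current status, so a participant who lapsed and returned counts as in care. Viral load comes from medical records rather than the interview, and visit counts are descriptive only. No effect of a two- to three-week shift on social support, knowledge or adherence can be derived from the documents.

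A reader might infer that the primary result or the 12-month proportion is biased. Neither follows, for the reasons in step 5. A reader might also single out the first person enrolled in a slow LGA and obtain a larger figure. That is one person's probability and should not be set against a 12.5-point difference between groups.

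**Conclusion.** The concern holds in conditional form. The protocol uses inconsistent anchors, and one of them does not exist for controls. If that one is followed and controls are timed from enrolment, the SAP's endline status, the analyses built on it and the interview-based secondary outcomes are compared after unequal time since baseline. The tilt on measured retention is against the intervention.

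On the protocol's constant 12-month rates and an assumed mean wait of about 2 to 3 weeks, the size is roughly 1 to 2 points of cumulative retention. It is somewhat more if endline falls at 6 to 9 months on the same rates, and about 1 point or less at 12 months if loss slows as the Background reports. The wait, the accrual pattern and the use of first loss in place of current status are all assumptions.

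The documents do not show that the arms will be timed differently, only that nothing prevents it. The proportion retained 12 months after enrolment is unaffected. The day-270 log-rank test keeps the same origin and horizon in both arms and is affected only if closing dates before day 270 differ by arm. The point is worth correcting because the remedy costs almost nothing.

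**What to change.** 1. Protocol, Structured questionnaires: time the six-month and endline interviews from enrolment (the baseline date) in both arms, with one common window. Bring the wording in Design into line.
2. SAP IV.C: set the endline reference for care status and visit counts at one fixed number of days after baseline for every participant, interviewed or not. The interview date and the pooled median are then no longer needed for this purpose.
3. Report the baseline-to-endline interview interval by arm, so that any remaining imbalance in the questionnaire outcomes is visible.

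The cost is a small protocol wording change and a change of reference date in the SAP code. No new data are needed, because clinic visit dates are already abstracted. The downside is that interviews in late-starting groups fall slightly sooner after the sessions end.

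A log-rank test started at group launch would not be a good alternative. It would drop losses during the wait, when the Background shows loss is most frequent, and it would need invented launch dates for controls.
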